4.5.1.2 EXTREME Regimen (Arm B)

Participants randomized to Arm B will receive treatment with an initial dose of cetuximab 400 mg/m² (over 2 hours infusion) then weekly 250 mg/m² (over 1 hour infusion) (or every 2 weeks, per local prescribing information), cisplatin (100 mg/m² IV on Day 1) or carboplatin (AUC 5 IV on Day 1) and 5-FU (1000 mg/m² continuous IV from Day 1 to Day 4) every 3 weeks per cycle for a maximum of 6 cycles.

Cetuximab maintenance begins after 6 cycles of the cetuximab, cisplatin or carboplatin, and 5-FU are complete and is considered cetuximab alone at 250 mg/m² weekly (1 hour infusion). Cetuximab maintenance can continue until progression, unacceptable toxicity, withdrawal of consent, or other reason (see [Section 3.5](#) for complete list of reasons for discontinuing study medication).

The dosing calculations should be based on the body weight. If the participant's weight on the day of dosing differs by > 10% from the weight used to calculate the dose, the dose must be recalculated. Doses can be rounded per institutional standards. Participants may be dosed no less than 7 days between doses.

The dose of Carboplatin during chemotherapy will be calculated using the following formula (Calvert equation):

- Carboplatin total dose in mg = AUC x (glomerular filtration rate [GFR] +25)

NOTE: When calculating carboplatin dose, GFR should not exceed 125 mL/min. Thus, the maximum carboplatin dose for AUC of 5 will be 750 mg.

Calculated creatinine clearance (CrCl) will be used to estimate the GFR. The modified Cockcroft-Gault formula below should be used to calculate the creatinine clearance.

- $140 - \text{age (years)} \times \text{actual weight (kg)} / 72 \times \text{Serum creatinine (mg/dL)}$ (for females, multiply the result by 0.85)

The actual weight will be used for the calculation of Creatinine Clearance.

If one of the study drugs is discontinued, the other study drugs may be continued for the remainder of the cycles.

Premedications

For cetuximab:

The recommended premedication is with an H1 antagonist (eg, 50mg Diphenhydramine) IV 30-60 minutes prior to the first dose; for subsequent doses, premedication should be administered based upon clinical judgement and presence/severity of prior infusion reactions in accordance with local institutional standard practice.

For carboplatin or cisplatin:

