Cumulative Dose	Cum dose $(mg/m^2)$ is sum of the doses $(mg/m^2)$ administered to a subject.	Cum dose $(mg/m^2)$ is sum of the doses $(mg/m^2)$ administered to a subject.
Relative dose intensity (%)	[Cum dose (mg/m²) - initial dose of cetuximab(mg/m²) ]/[(Last Cetuximab dose date - Cetuximab Start dose date )x250/7] x 100	Cum dose (mg/m²)/[(First dose date of 5-FU in Last Cycle - 5-FU Start dose date + 21) x 4000/21] x 100
Duration of treatment (overall)	Last dose date - Start dose date +1	Last dose date - Start dose date +1

**Table 7.4.1-3:** Study Therapy Parameter Definitions- Cisplatin/Carboplatin

	Cisplatin	Carboplatin	
Dosing schedule per protocol	100mg/ m  on day 1 every 3 weeks	AUC 5 on day 1 of every 3 week	

Cisplatin Carboplatin Dose Dose  $(mg/m^2)$  is defined as Total Dose (AUC) is defined as Total Dose administered (mg)/Most re-Dose administered (mg)/(creatinine cent BSA. Dose administered in mg clearance +25). Dose administered at each dosing date is collected on in mg at each dosing date is colthe CRF and BSA is derived from lected on the CRF and creatinine clearance derived from the CRF most recent weight and baseline height also collected on the CRF. data. Cumulative Dose Cum dose  $(mg/m^2)$  is sum of the Cum dose (AUC) is sum of the doses (mg/m²) administered to a doses (AUC) administered to a sub-

Cum dose (mg/m²)/[(Last Cisplatin

dose date - Cisplatin Start dose date

Last dose date - Start dose date +1

+ 21) x 100/21] x 100

ject.

Cum dose (AUC)/[(Last dose date

of Carbo - Start dose date of Carbo

Last dose date - Start dose date +1

+ 21) x 5/21] x 100

Table 7.4.1-3: Study Therapy Parameter Definitions- Cisplatin/Carboplatin

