#### 7.4.2.4 Dose Reductions

Dose reductions (within subject) are not permitted for either nivolumab or ipilimumab. Therefore, no analyses on dose reductions will be presented for these two agents.

Up to two dose level reductions are allowed for cetuximab, cisplatin, carboplatin and 5-FU. The dose levels for each of these drugs are defined in the protocol as follows:

Table 7.4.2.4-1: Dose Levels for Cetuximab, Cisplatin, Carboplatin and 5-FU

	Cetuximab (mg/m2)	Cisplatin (mg/m2)	Carboplatin (AUC)	5-FU (mg/m2/day)
Starting Dose	250*	100	AUC 5.0	1000
Dose Level -1	200	75	AUC 4.0	750
Dose Level -2	150	56	AUC 3.0	560
Dose Level -3	Stop drug	Stop drug	Stop drug	Stop drug

\*The dose level of cetuximab is 400 mg/m2 for the first dose and 250 mg/m2 afterwards.

For any cycle, it will be defined as a dose reduction if the observed dose level (based on calculated administered dose) is below the dose level of the previously administered dose. Dose ranges for dose levels of platinum doublet chemotherapy are defined in Table 7.4.2.4-2.

Table 7.4.2.4-2: Calculated Dose Ranges and Related Dose Levels

Dose Level	Dose Range			
	Cetuximab (mg/m2)	Cisplatin (mg/m2)	Carboplatin (AUC)	5-FU (mg/m2/day)
Level 0	≥225	≥87.5	≥4.5	≥875
Level -1	<225 and ≥ 175	$< 87.5 \text{ and } \ge 65.5$	<4.5 and ≥3.5	<875 and $≥655$
Level -2	<175	<65.5	<3.5	<655

The reason for dose reduction as reported by the investigator will be tabulated for all instances of dose reduction based on the Dose Change CRF page. A category 'Unknown' will be defined for all reductions with no reason reported by the investigator.

The following will be summarized for chemotherapeutic agent arm only:

• Number and percentage of subjects with at least one dose reduction and reason of the dose reduction, number and percentage of subjects with a dose reduction to dose level -1, number and percentage of subjects with a dose reduction to dose level -2.

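### SAP Table 7.4.1-3 back-calculates carboplatin AUC without the protocol's 125 mL/min GFR cap, so compliant doses at clearance above 125 are shown as less than AUC 5

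*SAP*

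**What the plan says.** **Dosing (protocol section 4.5.1.2).** The dose follows the Calvert equation: "Carboplatin total dose in mg = AUC x (glomerular filtration rate [GFR] +25"). The GFR input is specified: "Calculated creatinine clearance (CrCl) will be used to estimate the GFR". It is limited: "When calculating carboplatin dose, GFR should not exceed 125 mL/min". The protocol draws the consequence itself: "Thus, the maximum carboplatin dose for AUC of 5 will be 750 mg".

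**Analysis (SAP section 7.4.1, Table 7.4.1-3).** The extracted text interleaves the cisplatin and carboplatin cells: "Dose administered (mg)/(creatinine cent BSA. Dose administered in mg clearance +25"). The carboplatin formula can still be recovered, because only carboplatin is expressed as AUC or uses clearance plus 25: AUC equals total mg divided by (creatinine clearance + 25). The clearance input is "lected on the CRF and creatinine clearance derived from the CRF" data. No upper limit is given here or elsewhere in the SAP.

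**Where that AUC goes.** It is summed to the cumulative dose and compared with AUC 5 every 21 days to give RDI, which section 7.4.1 reports in categories with cut-points at 50, 70, 90 and 110%. It also sets the dose level in Table 7.4.2.4-2: Level 0 at 4.5 or more, Level -1 from 3.5 to below 4.5, Level -2 below 3.5. Section 7.4.2.4 then says that "it will be defined as a dose reduction if the observed dose level (based on calculated administered dose) is below the dose level of the" preceding dose. Reductions for which the investigator gave no reason are tabulated as Unknown.

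**The concern.** The SAP inverts the dosing equation with a different denominator from the one used to set the dose. Up to 125 mL/min the two agree. Above it, the milligrams stop rising while the SAP denominator keeps growing, so a dose given exactly as the protocol prescribes is converted to less than AUC 5.

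At stake is the description of how fully the control regimen was delivered, which readers of an open-label comparison will look at. Because the milligrams are capped and the denominator is not, the error in AUC and RDI for a compliant dose runs one way: carboplatin delivery can be understated but not overstated.

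**Working it through.** **Inputs.** From protocol 4.5.1.2: mg = AUC x (GFR + 25), GFR at most 125. From SAP Table 7.4.1-3: AUC = mg / (CrCl + 25), and RDI = cumulative AUC / [(last date - first date + 21) x 5/21] x 100. From SAP Table 7.4.2.4-2: level cut-points 4.5 and 3.5.

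**1. The protocol's own figure.** 5 x (125 + 25) = 750 mg, as stated.

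**2. RDI for on-time dosing.** For n cycles exactly 21 days apart the denominator is [21(n - 1) + 21] x 5/21 = 5n, so RDI is the mean AUC divided by 5, times 100.

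**3. SAP formula applied to a compliant AUC 5 dose.**

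| CrCl (mL/min) | Dose (mg) | SAP AUC | RDI | Level |
|---|---|---|---|---|
| 100 | 625 | 625/125 = 5.00 | 100% | 0 |
| 125 | 750 | 750/150 = 5.00 | 100% | 0 |
| 130 | 750 | 750/155 = 4.84 | 96.8% | 0 |
| 140 | 750 | 750/165 = 4.55 | 90.9% | 0 |
| 150 | 750 | 750/175 = 4.29 | 85.7% | -1 |
| 175 | 750 | 750/200 = 3.75 | 75.0% | -1 |
| 200 | 750 | 750/225 = 3.33 | 66.7% | -2 |

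With min(CrCl, 125) in the denominator, every row returns AUC 5.00, RDI 100% and Level 0.

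**4. Thresholds for a 750 mg dose.** AUC falls below 4.5, and RDI below 90%, when CrCl exceeds 750/4.5 - 25 = 141.7. AUC falls below 3.5, and RDI below 70%, when CrCl exceeds 750/3.5 - 25 = 189.3. Between 125 and 141.7 the continuous AUC and RDI are too low, but level and RDI category are unchanged.

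**5. When a false reduction is counted.** The level is compared with that of the previous dose, so clearance has to rise across 141.7 or 189.3 between cycles. Assumed patient: man, 50 years, 85 kg, with the protocol's Cockcroft-Gault formula read in its usual bracketing.
- Creatinine 0.8 mg/dL: 90 x 85 / (72 x 0.8) = 132.8. Dose 750 mg, SAP AUC 750/157.8 = 4.75, Level 0.
- Creatinine 0.7 mg/dL: 90 x 85 / (72 x 0.7) = 151.8. Dose 750 mg, SAP AUC 750/176.8 = 4.24, Level -1.

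The milligrams are identical, yet a reduction is recorded.

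**6. Real reductions.** The cap applies to the dose calculation generally, so AUC 4 is at most 4 x 150 = 600 mg. At a stable CrCl of 145, a genuine step from 750 to 600 mg gives 750/170 = 4.41 and then 600/170 = 3.53. Both are Level -1, so the reduction is missed. At 150, 600/175 = 3.43, and a one-level reduction is tabulated as Level -2.

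**The case against.** The case for treating this as small is reasonable, and most of it stands.

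- **Few participants may be affected.** The renal routes into carboplatin select low clearance: the protocol advises against cisplatin below 60 mL/min (section 3.3.2), allows a switch to carboplatin below 60 (4.5.5.3), and lists renal impairment among the reasons for substitution (4.5.1.2). On the other hand, the choice of platinum is left to the investigator, and a stated cap with a 750 mg maximum shows that clearances above 125 were foreseen.
- **The SAP is silent on a cap rather than explicitly uncapped.** True, but a programmer who follows the table as written will not apply one.
- **The artefact is partly visible.** By-subject dosing listings are planned, and derived reductions with no investigator reason fall under Unknown. That helps in reading the reduction counts; it does not correct RDI.
- **The cap is not the only source of apparent reductions.** Section 4.5.1.2 requires recalculation for a weight change above 10%; no passage requires it for creatinine alone. Assume 525 mg set at CrCl 80 (5 x 105) and repeated at CrCl 95: 525/120 = 4.38, Level -1. Capping at 125 does not change this.

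A reader might infer that fully dosed carboplatin participants in general will appear as dose-reduced. The documents do not support that: at or below 125 the formula returns exactly AUC 5, and a participant whose clearance is stable above 141.7 is shown as under-dosed but never as reduced.

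**Conclusion.** The mismatch is real, and the SAP formula is wrong as written for one subset: Arm B participants on carboplatin with creatinine clearance above 125 mL/min. For them a compliant dose gives AUC below 5 and RDI below 100%. RDI category and dose level change only above 141.7 mL/min, and again above 189.3. False reductions need a rise across one of those values between cycles.

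The size in this trial cannot be stated, because the documents do not give the share of carboplatin participants above 125. The per-participant figures assume on-time dosing at the protocol dose; the false-reduction example also assumes that clearance is re-derived for each dose, which the SAP does not specify.

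It would go too far to infer that comparator-arm exposure as a whole will be misreported, or that the efficacy comparison is compromised. The effect is confined to descriptive carboplatin exposure and dose-reduction tables. OS, alpha and power do not use this variable.

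**What to change.** In SAP Table 7.4.1-3, define carboplatin dose (AUC) as total dose administered in mg / [min(creatinine clearance, 125) + 25]. Use this value for cumulative dose, RDI and the dose levels of Table 7.4.2.4-2. This aligns the derivation with the protocol's dosing calculation and changes nothing in how participants are dosed.

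The cost is one formula and one line of programming, with all inputs already collected. SAP version 2.0 already corrected a number in this same table, so a further edit there is routine.

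The change removes the cap artefact only. Apparent reductions that arise when clearance changes and the milligram dose is not recalculated will remain, and the table should not be read as free of them.

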## 7.4.2 Modifications of Study Therapy

## 7.4.2.1 Dose Delays

Duration of treatment (overall)

Relative dose intensity (%)

Each of study drug infusions may be delayed. A dose will be considered as actually delayed if the delay is exceeding 3 days (i.e. greater than or equal to 4 days from scheduled dosing date) for nivolumab and ipilimumab. All study drugs must be delayed until treatment can resume. Reason for dose delay will be retrieved from CRF dosing pages.

The following parameters will be summarized by treatment group:

subject.

• Number of subjects with at least one dose delayed, the number of dose delays per subject, the reason for dose delay and the length of dose delay.

#### 7.4.2.2 Infusion Interruptions and Rate Changes

Each of study drug infusions can be interrupted and/or the IV infusion rate can be reduced. This information will be retrieved from CRF dosing pages.

The following parameters will be summarized by treatment group:

- Number of subjects with at least one dose infusion interruption, the reason for interruption, and the number of infusion interruptions per subject.
- Number of subjects with at least one IV infusion rate reduction, the reason for reduction and the number of infusion with IV rate reduction per subject.

#### 7.4.2.3 Dose Escalations

Dose escalations (within subject) are not permitted for either nivolumab or ipilimumab.

#### 7.4.2.4 Dose Reductions

Dose reductions (within subject) are not permitted for either nivolumab or ipilimumab. Therefore, no analyses on dose reductions will be presented for these two agents.

Up to two dose level reductions are allowed for cetuximab, cisplatin, carboplatin and 5-FU. The dose levels for each of these drugs are defined in the protocol as follows:

Table 7.4.2.4-1: Dose Levels for Cetuximab, Cisplatin, Carboplatin and 5-FU

	Cetuximab (mg/m2)	Cisplatin (mg/m2)	Carboplatin (AUC)	5-FU (mg/m2/day)
Starting Dose	250*	100	AUC 5.0	1000
Dose Level -1	200	75	AUC 4.0	750
Dose Level -2	150	56	AUC 3.0	560
Dose Level -3	Stop drug	Stop drug	Stop drug	Stop drug

\*The dose level of cetuximab is 400 mg/m2 for the first dose and 250 mg/m2 afterwards.

For any cycle, it will be defined as a dose reduction if the observed dose level (based on calculated administered dose) is below the dose level of the previously administered dose. Dose ranges for dose levels of platinum doublet chemotherapy are defined in Table 7.4.2.4-2.

Table 7.4.2.4-2: Calculated Dose Ranges and Related Dose Levels

Dose Level	Dose Range			
	Cetuximab (mg/m2)	Cisplatin (mg/m2)	Carboplatin (AUC)	5-FU (mg/m2/day)
Level 0	≥225	≥87.5	≥4.5	≥875
Level -1	<225 and ≥ 175	$< 87.5 \text{ and } \ge 65.5$	<4.5 and ≥3.5	<875 and $≥655$
Level -2	<175	<65.5	<3.5	<655

The reason for dose reduction as reported by the investigator will be tabulated for all instances of dose reduction based on the Dose Change CRF page. A category 'Unknown' will be defined for all reductions with no reason reported by the investigator.

The following will be summarized for chemotherapeutic agent arm only:

• Number and percentage of subjects with at least one dose reduction and reason of the dose reduction, number and percentage of subjects with a dose reduction to dose level -1, number and percentage of subjects with a dose reduction to dose level -2.

#### 7.4.2.5 Dose Omissions

Dose omissions are not permitted.

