4.5.2.1 Nivolumab and Ipilimumab (Arm A)

Dose delay criteria apply for all drug-related AEs. Treatment delay is up to 6 weeks for nivolumab and up to 12 weeks for ipilimumab from the last dose are allowable (any dose delays greater than these will require approval from the medical monitor). It is permissible in cases of a dose held due to AE to skip the dose in the cycle in order to bring the patient back on track with the next Cycle visit.

Tumor assessments for all participants should continue as per protocol even if dosing is delayed.

Nivolumab and ipilimumab administration should be delayed for the following:

- Grade 2 non-skin, drug-related AE, with the exception of fatigue
- Grade 2 drug-related creatinine, AST, ALT and/or Total Bilirubin abnormalities
- Grade 3 skin, drug-related AE
- Grade 3 drug-related laboratory abnormality, with the following exceptions:
 - Grade 3 lymphopenia or asymptomatic amylase or lipase does not require dose delay
 - Grade ≥ 3 AST, ALT, Total Bilirubin will require dose discontinuation (see section 4.5.5)
- Any adverse event, laboratory abnormality, or intercurrent illness which, in the judgment of the investigator, warrants delaying the dose of study medication.
- Participants receiving ipilimumab in combination with nivolumab that have drug-related toxicities that meet the criteria for dose delay, should have both drugs (ipilimumab and nivolumab) delayed until retreatment criteria are met. (Exceptions apply to the retreatment criteria after dose delay of ipilimumab and nivolumab for Grade ≤ 3 amylase and lipase

abnormalities that are not associated with symptoms or clinical manifestations of pancreatitis and that are attributed to ipilimumab alone.)

- Participants who require delay of nivolumab should be re-evaluated weekly or more frequently if clinically indicated and resume nivolumab dosing when re-treatment criteria are met.

Rescheduling:

- Nivolumab may be delayed until the next planned ipilimumab dose if the next ipilimumab dose is scheduled within the next 12 days. This will permit periodic ipilimumab dosing to be synchronized with nivolumab dosing.

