4.5.2.2 EXTREME Regimen

It is permissible in cases of a dose held due to AE to skip the dose in the cycle in order to bring the patient back on track with the next Cycle visit. Cetuximab, cisplatin, carboplatin, and 5-FU should be delayed for the following:

- Presence of febrile neutropenia or neutropenia < 1500 cells/mm³ for greater than one week despite the use of Growth factors
- Any Grade ≥ 2 non-skin, drug-related adverse event, except for alopecia, fatigue or laboratory abnormalities
- Any Grade 3 skin drug-related AE
- Any Grade 3 drug-related laboratory abnormality, with the following exceptions:
 - Grade 3 lymphopenia does not require a dose delay
 - Delay if total bilirubin $> 1 \times$ ULN or if AST and/or ALT $> 1.5 \times$ ULN occurs concomitant with alkaline phosphatase $> 2.5 \times$ ULN
- Any AE, laboratory abnormality or inter-current illness which, in the judgment of the investigator, warrants skipping the dose of study medication.

Subsequent dose reductions may be required as per [Section 4.5.3.2](#). Participants may receive growth factors (including G-CSF and erythropoietin) at the discretion of the investigator.

A dose given more than 3 days after the intended dose date will be considered a dose delay. A maximum delay of 6 weeks between doses is allowed. Longer delays may be allowed following discussion with the Medical Monitor.

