4.5.3.2 EXTREME Regimen

This section includes information on dose modifications for cetuximab, cisplatin or carboplatin and 5-FU treatment related toxicities.

A maximum of 2 dose reductions per study drug are permitted; if additional reductions are required, that particular study drug must be discontinued. Once a dose has been decreased, it should remain reduced for all subsequent dosing unless dose is further reduced. No dose escalations will be allowed. If one of the study drugs is delayed due to drug related toxicities during a treatment cycle, the other study drugs in the regimen may be administered at the discretion of the investigator; when dosing is resumed, dose reduction should only be applied to the study drug that was withheld.

Participants who discontinue one of the study drugs may, at the investigators discretion continue administration of the other study drugs in the regimen.

For Cetuximab: Dose modifications are permitted, as follows:

Infusion Reactions:

- Reduce the infusion rate by 50% for NCI CTC Grade 1 or 2 and non-serious NCI CTC Grade 3 infusion reactions.
- Immediately and permanently discontinue cetuximab for serious infusion reactions, requiring medical intervention and/or hospitalization.
- See [Section 4.5.8.2](#) for treatment of Cetuximab Infusion Reactions.

Dermatologic Toxicity: Table 4.5.3.2-1 contains the recommended dose modifications for severe (CTCAE v4 Grade 3 or 4) acneiform rash.

Table 4.5.3.2-1: Cetuximab Dose Modification Guidelines for Rash			
Severe Acneiform Rash	Cetuximab	Outcome	Cetuximab Dose Modification
1 st Occurrence	Delay infusion 1 to 2 weeks	Improvement No Improvement	Continue at 250 mg/m ² Discontinue Cetuximab
2 nd Occurrence	Delay infusion 1 to 2 weeks	Improvement No Improvement	Continue at 200 mg/m ² Discontinue Cetuximab
3 rd Occurrence	Delay infusion	Improvement	Continue at 150 mg/m ²

Table 4.5.3.2-1: Cetuximab Dose Modification Guidelines for Rash			
Severe Acneiform Rash	Cetuximab	Outcome	Cetuximab Dose Modification
	1 to 2 weeks	No Improvement	Discontinue Cetuximab
4 th Occurrence	Discontinue Cetuximab permanently		

For Cisplatin, Carboplatin and 5-FU:

Recommendations for dose modifications for cisplatin, carboplatin and 5-FU should be considered with local institutional standards. The dose levels for 5-FU, cisplatin and carboplatin are listed in Table 4.5.3.2-2:

Table 4.5.3.2-2: Dose Levels for 5-FU, Cisplatin, and Carboplatin

	5-FU Dose	Cisplatin Dose	Carboplatin Dose

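### For Arm B the SAP rules out dose omissions and single-drug holds that the protocol allows, so the delay summary may count skipped doses as delays and no table shows omissions

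*SAP*

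**What the plan says.** **SAP**

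- 7.4.2.5 is a single sentence: "Dose omissions are not permitted". It names no arm or drug, and no omission summary follows.
- 7.4.2.1 opens by saying that any study drug infusion may be delayed. It counts a dose as delayed when the delay is "greater than or equal to 4 days from scheduled dosing date) for nivolumab and ipilimumab", and gives no threshold for the Arm B drugs. It then states: "All study drugs must be delayed until treatment can resume", again without naming an arm. The planned output is "Number of subjects with at least one dose delayed, the number of dose delays per subject, the reason for dose delay and the length of" the delay, by treatment group.

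**Protocol, Arm B**

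- 4.5.2.2: "It is permissible in cases of a dose held due to AE to skip the dose in the cycle", so that the patient is back on schedule at the next cycle visit. The same section lists events that, in the investigator's judgment, give a reason that "warrants skipping the dose of study medication". It treats a dose given more than 3 days late as a delay.
- 4.5.3.2: when one drug is delayed for toxicity, "the other study drugs in the regimen may be administered at the discretion of the investigator".
- 4.5.4.3: after a Grade 3 skin reaction, cetuximab is withheld for as many as two infusions in a row.

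**Protocol, Arm A**

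- 4.5.2.1 gives the same permission to skip a held dose as 4.5.2.2, but 4.5.1.1 says that dosing visits are delayed and never skipped.
- 4.5.2.1 also says that participants who meet the delay criteria "should have both drugs (ipilimumab and nivolumab) delayed until retreatment criteria are met". 4.5.4.2 makes an exception: for certain amylase or lipase abnormalities, nivolumab may restart before ipilimumab.

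**The concern.** The SAP's rules on omission and joint delay decide what is programmed. SAP 7.4.2.4 shows how such wording works: because reductions of nivolumab and ipilimumab are ruled out, it plans no reduction analysis for them. By the same logic, 7.4.2.5 leaves omissions without an output, although the protocol provides for them in Arm B.

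A programmer who follows the SAP then has no category for a skipped dose. If a later dose is given, the gap looks like a long delay. If none is given, nothing appears. For Arm B drugs it is not even stated how late a dose must be to count as delayed.

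At stake is the description of how each regimen was delivered. Safety and tolerability in both arms is a stated exploratory objective, and delays, omissions and reductions by drug are part of reading it. The efficacy analyses do not use these tables.

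**Working it through.** The plan gives no figure on this point, so there is none to reproduce. The check has two parts.

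**1. The passages side by side**

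| Topic | SAP | Protocol, Arm B | Protocol, Arm A |
|---|---|---|---|
| Skipping a held dose | Ruled out (7.4.2.5) | Allowed (4.5.2.2) | Allowed (4.5.2.1) and ruled out (4.5.1.1) |
| Holding one drug while others continue | Ruled out (7.4.2.1) | Allowed (4.5.3.2); cetuximab alone withheld (4.5.4.3) | Both held together (4.5.2.1), with an amylase/lipase exception (4.5.4.2) |
| Delay threshold | More than 3 days, nivolumab and ipilimumab only (7.4.2.1) | More than 3 days (4.5.2.2) | More than 3 days (4.5.2.1) |

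The Arm B column conflicts with the SAP on the first two rows, and its threshold is not carried over on the third. In the Arm A column the SAP agrees with one of two conflicting protocol statements on skipping, and with the general rule on joint delay.

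**2. What the planned outputs would show**

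The relative dose intensity (RDI) formulas are those of SAP Tables 7.4.1-1 to 7.4.1-3. The dose dates are illustrative assumptions, with every dose given in full.

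*Nivolumab*, 10 planned doses on days 0, 14, …, 126. RDI = cumulative dose / [(last date − first date + 14) × 3/14] × 100.

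- Fifth dose (day 56) skipped: 9 × 3 = 27 mg/kg given; (126 + 14) × 3/14 = 30 planned; RDI = 90.0%.
- Nine-dose course with doses 5 to 9 each 14 days late: the dose dates are identical, so RDI is again 90.0%. Against the SAP threshold, the gap of 28 days less the 14-day interval is a delay of 14 days.
- Tenth dose skipped: 27 given; (112 + 14) × 3/14 = 27 planned; RDI = 100%, and no delay is visible.

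*Cisplatin*, 6 planned cycles on days 0, 21, …, 105. RDI = cumulative dose / [(last − first + 21) × 100/21] × 100.

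- Cycle 3 omitted: 500 / [(105 + 21) × 100/21 = 600] = 83.3%. The apparent delay is 42 − 21 = 21 days.
- Cycle 6 omitted: 500 / [(84 + 21) × 100/21 = 500] = 100%.

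*Cetuximab*, 18 planned weekly doses on days 0, 7, …, 119. RDI = (cumulative dose − initial dose) / [(last − first) × 250/7] × 100.

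- One mid-course dose skipped: 16 × 250 = 4,000; 119 × 250/7 = 4,250; RDI = 94.1%. The apparent delay is 14 − 7 = 7 days. Two infusions withheld in a row would appear as 21 − 7 = 14 days.

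RDI therefore shows the shortfall from a mid-course skip but cannot say that it was a skip. Neither RDI nor the delay summary shows a skip of the last planned dose.

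**The case against.** The best defence of the SAP is that its two sentences have a source. Protocol 4.5.1.1 supports the ban on omissions for Arm A, and 4.5.2.1 supports joint delay of nivolumab and ipilimumab. In SAP 7.4.2.1 the joint-delay sentence directly follows a threshold for those two drugs, so it can be read as the Arm A rule. That section also says that any infusion may be delayed, so a single-drug hold could still be recorded. All of this stands for Arm A. It does not help for Arm B, where the protocol permits skipping and single-drug holds and the SAP states no exception.

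Four stronger readings are tempting, and the documents do not support them.

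- *The SAP contradicts the protocol in both arms.* For Arm A the protocol contradicts itself on skipping, and the SAP follows one side.
- *The exposure tables will miss skipped doses.* SAP 7.4.1 summarises number of doses, cumulative dose and RDI for each drug and adds a by-subject dosing listing. Most skips lower these figures.
- *The distortion is larger in Arm B because cetuximab is weekly.* Over 18 weeks there are about 18 cetuximab doses against 9 of nivolumab, but that is only dosing frequency. At an equal rate per dose, the share of planned doses missed is the same, and the documents give no omission rate.
- *Reasons for omission are already on the CRF.* The SAP mentions CRF reasons for delay, infusion interruption, rate reduction, dose reduction and partial discontinuation, but not for omission.

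**Conclusion.** The point holds for Arm B: SAP 7.4.2.5 and the joint-delay sentence in 7.4.2.1 state rules that protocol 4.5.2.2, 4.5.3.2 and 4.5.4.3 contradict, and the protocol's Arm B delay definition is not carried over. For Arm A, protocol 4.5.1.1 and 4.5.2.1 must be reconciled with each other before the SAP can be judged on skipping. The joint-delay sentence fits the general Arm A rule but not the amylase/lipase exception.

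The size is small and confined to reporting. Under the assumed schedules, a single mid-course skip may be counted as a delay of 7 days (cetuximab), 14 days (nivolumab) or 21 days (cisplatin), and a skip of the final dose is not seen. How often this would happen cannot be estimated from the documents. The overall survival analyses and the alpha allocation are unaffected. The mock-ups are in the Data Presentation Plan, which is not among the documents, so a table there may already separate the two. If so, the SAP text still needs correcting.

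**What to change.** 1. Reconcile protocol 4.5.1.1 with 4.5.2.1 on skipping in Arm A, and the SAP with the protocol in both arms. No view is taken here on which dosing rule should stand.
2. In SAP 7.4.2.1, define delay separately for each drug, carry over the protocol's more-than-3-day definition for Arm B, limit the joint-delay sentence to Arm A with its amylase/lipase exception, and exclude omitted doses from delay counts and lengths.
3. Replace SAP 7.4.2.5 with a by-drug summary: number and percentage of subjects with at least one omitted dose, and the number of doses omitted, derived from dosing dates, with reasons where the CRF records them.
4. State the derivation rule, because dates alone do not separate a skip from a delay of one full interval. The rule should use the schedule in force, since cetuximab maintenance may be every 2 weeks, and say how a missing final dose is handled. In Arm B, the dates of the other drugs in the same cycle can help identify a single-drug omission.

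The cost is a wording change in two SAP subsections, a clarification of the Arm A text in the protocol, and one more exposure table. The dosing dates are already needed for the planned exposure tables. Omission reasons come at no extra cost only if the CRF already captures them.
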